6.10 Dosing Diary

The subject/parent/guardian (caregiver) will be provided with an electronic dosing diary to record the time and amount of each study drug application. The importance of adherence to the study schedule will be reinforced at each study visit.

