11.3.3 Treatment Compliance

The Parent/guardian (caregiver)/Subject will record all applications made or missed in the electronic diary. Subject compliance during the overall treatment period and by visit will be summarized.

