11.3.4 Drug Exposure

Amount of study drug (weight) and the number of days with study drug application will be summarized.

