5. CHANGES IN THE CONDUCT OF THE STUDY OR PLANNED ANALYSES

There are no changes in the conduct of the study or planned analyses.

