7.9.9 Safety Analyses

7.9.9.1 Extent of Exposure

The extent of exposure to study drug will be summarized by total number of days of exposure, total number of applications, percent compliance, and total amount of study drug applied. Total number of applications will be determined by the number of entries in the dosing diary. Total number of days of exposure will be computed as follows:

Days of Exposure = Date of Last Application – Date of First Application + 1.

To compute percent compliance, total number of expected applications will be calculated by:

Expected applications = $2 * (\text{Study Completion/Discontinuation Date} - \text{Date of First Application})$.

If the total number of expected applications exceeds 58 then it will be set to 58. Percent compliance will be calculated from total number of applications and total number of expected applications as follows:

Percent Compliance = $100 * (\text{Total Applications}/\text{Expected Applications})$.

Percent compliance will not be calculated for subjects who are lost to follow-up.

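### The SAP reports a first-to-last calendar span as days of exposure, whereas the protocol promises a count of days on which drug was applied; the change is undeclared and its effect is minor.

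*SAP*

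**What the plan says.** Protocol 11.3.4 defines the exposure summary in one sentence: "Amount of study drug (weight) and the number of days with study drug application will be summarized". The data for it are collected. Protocol 6.10 gives families an "electronic dosing diary to record the time and amount of each study drug application", and Protocol 11.3.3 says that they "will record all applications made or missed in the electronic diary".

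SAP 7.9.9.1 says that exposure will be "summarized by total number of days of exposure, total number of applications, percent compliance, and total amount of study drug applied". It then fixes the first of these: the words "Total number of days of exposure will be computed as follows" lead into the formula "Days of Exposure = Date of Last Application – Date of First Application + 1". Nothing is subtracted for dates without an application, and no other visible SAP output counts treated dates.

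Protocol 11.3.1 makes the SAP the place where modifications to the planned analysis are to appear. SAP section 5 states: "There are no changes in the conduct of the study or planned analyses".

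**The concern.** The two documents name different quantities. The protocol's is a count of treated dates. The SAP's is the calendar distance between the first and last treated dates. A child who applied ointment every day and a child who paused and resumed get the same SAP value if their first and last dates match. Since section 5 declares no change, a reader of the report would take the SAP figure for the one the protocol promised.

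What is at stake is the accuracy of one line in the exposure summary. That line has some descriptive value here, because the study is meant to show exposure under maximal use and SAP 4.1.2 plans only about 8 children in each of the two younger groups. One child's interrupted treatment is therefore a visible share of a group.

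**Working it through.** **Inputs.** Planned treatment is twice daily on 28 consecutive days (Protocol 8.4). The SAP formula and the protocol measure are as quoted above. The gap patterns and miss probabilities below are assumptions, because the documents give none.

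**Formulas.** SAP value = last date - first date + 1. Protocol value = number of distinct dates with at least one application. Excess = SAP value - protocol value, which equals the number of interior dates with no application.

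**Full adherence.** First dose on Day 1, last on Day 28: 28 - 1 + 1 = 28, and the count of treated dates is also 28. The formula reproduces the planned duration when there are no gaps.

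| Pattern (first dose Day 1) | Treated dates | SAP value | Excess |
|---|---|---|---|
| Days 1-28, no gap | 28 | 28 | 0 |
| One dose a day on all 28 days | 28 | 28 | 0 |
| Permanent stop after Day 14 | 14 | 14 | 0 |
| 3 untreated interior days, last dose Day 28 | 25 | 28 | 3 |
| Days 1-10 and 15-28 | 10 + 14 = 24 | 28 | 4 |
| 7 untreated interior days, last dose Day 28 | 21 | 28 | 7 |

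In the fifth row, 28/24 = 1.17, so the SAP value is 17% too high. This pattern is compatible with dosing at every nominal clinic visit (Days 1, 8, 15 and 22).

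**Typical size under random misses.** If each application is missed independently with probability m, a date is wholly untreated with probability m². Over 28 dates the expected number is 28 × m²:

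- m = 5%: 28 × 0.0025 = 0.07 days
- m = 10%: 28 × 0.01 = 0.28 days
- m = 20%: 28 × 0.04 = 1.12 days

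These are slightly high, because the first and last treated dates cannot be gaps. With 26 interior dates the last figure is 26 × 0.04 = 1.04. Only clustered gaps produce a larger error.

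**Do the companion summaries recover the count?** Take a final visit on Day 29. Expected applications are 2 × (29 - 1) = 56. The child treated on Days 1-10 and 15-28 makes 24 × 2 = 48 applications, or 48/56 = 86%. A child treated on all 28 days who misses a single dose on 8 of them makes 20 × 2 + 8 × 1 = 48, also 86%. The SAP would report both children with 28 days, 48 applications and 86% compliance, although treated days are 24 and 28.

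**The case against.** The best defence is that little depends on this line. Days of exposure enters neither the concentration summaries nor Cmax, Tmax or AUC in SAP 7.9.7. The adverse event tables in SAP 7.9.9.2 count subjects and are not adjusted for exposure time. Total applications, percent compliance and amount applied stand beside it, so a long gap would show as low compliance: 7 wholly untreated days give 42/56 = 75%. The protocol foresees no pause and resumption, since the reasons for stopping drug listed in 4.6.1.1 are permanent.

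Most of this stands, and it is why the point is minor. It does not remove the mismatch. As shown above, the companion summaries signal a shortfall without saying whether whole days went untreated. They may signal less than they appear to: the SAP counts diary entries as applications, while the diary also records missed ones, and the documents do not say whether a miss creates an entry.

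A reader might infer more than the documents support:

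- *Any missed day inflates the figure.* It does not. Days after a permanent stop and days with one dose missed cause no error.
- *The error could exceed 50%.* Treatment on Days 1-10 and 21-28 gives 18 treated days against 28 (28/18 = 1.56), but that pattern skips the Day 15 clinic application. It cannot serve as context for the Day 15 profile.
- *Adverse event rates or PK results would be biased.* No planned calculation in the visible text uses this figure.
- *The protocol promised a count up to Day 15.* Section 11.3.4 does not divide the count by period.

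**Conclusion.** Wrong as written (minor). SAP 7.9.9.1 substitutes a calendar span for the count of treated days in Protocol 11.3.4, and section 5 does not disclose it. The span is too high by exactly one day for each wholly untreated date between first and last application, and otherwise correct.

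The exact rule follows from the two texts alone. The sizes do not: 4 days (17%) rests on an illustrative gap, and 0.07 to 1.1 days rests on independent misses at 5-20%. Neither is a forecast. The consequence is confined to the descriptive exposure summary. The primary PK analysis and the planned adverse event tables are unaffected.

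**What to change.** In SAP 7.9.9.1, define days of exposure as the number of distinct diary dates with at least one application actually made, so that entries recording a missed dose do not count. Keep the present formula if wanted, relabelled as duration of treatment. If the sponsor prefers the span alone, section 5 should declare the departure from Protocol 11.3.4.

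As an optional addition, report the same count from Day 1 to the Day 15 clinic application. It would be a new supporting summary for the steady-state profile, not something the protocol already requires.

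The cost is a line or two of SAP text and a distinct-date count in the code. The diary already records the time of each application, so no new data are needed.

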7.9.9.2 Adverse Events

Treatment-emergent AEs (TEAEs) are defined as AEs with an onset on or after the date of the first study drug application. Treatment-emergent AEs will be summarized by system organ class and preferred term and further by severity and relationship to study drug. When summarizing AEs by severity and relationship, each subject will be counted once within a system organ class

or preferred term by using the event with the highest severity and strongest relationship within each classification.

Serious AEs (SAEs) will be summarized by system organ class, preferred term, severity, and relationship to study drug. Application site AEs and any TEAEs reported by $\geq 5\%$ of subjects will be summarized by system organ class and preferred term. Adverse events leading to treatment or study discontinuation will be summarized by system organ class and preferred term.

Listings will be presented for all adverse events as well as for serious adverse events, and adverse events leading to discontinuation from the study.

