10.3 Reporting Period

Serious adverse events require immediate notification to the Sponsor or designee, beginning from the time that the informed consent is signed, which is obtained prior to participation in the study, i.e., prior to undergoing any study-related procedure and/or receiving study drug, through and including the day of the last dose of study drug or longer as applicable. Any serious adverse event occurring any time within the reporting period must be promptly reported if a causal relationship to investigational product is suspected.

- Adverse events (serious and non-serious) should be recorded on the eCRF from the time the study subject has signed informed consent (assent) through last study visit, unless otherwise specified.
- Any changes in the subject's status between enrollment (signing informed consent) up to the time of the first dose of study drug will be recorded as a pre-treatment adverse event and severity will be assessed.

- Any adverse event occurring after the first dose of study drug will be considered a treatment emergent adverse event (TEAE).

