11.5 Secondary Analysis

11.5.1 Safety

Safety evaluations will consist of adverse events (AEs), application site reactions, physical examinations, vital signs, ECGs, weight, and laboratory measurements (hematology, chemistry, and urinalysis). Full details will be specified in the SAP. A general description of the planned analysis is as follows:

- Descriptive statistics and frequency tables will be prepared as appropriate for physical examinations, vital signs, weight, ECG (HR, QTcF, PR, and QRS) and laboratory measurements (hematology, chemistry, and urinalysis).
- Adverse Events
 - AEs will be coded using the Medical Dictionary for Regulatory Activities (MedDRA); the version will be identified in the clinical study report.
 - AEs that occurred during the screening period will be listed separately and will not be included in the AE tabulations.
 - All other AEs that start on or after first dose will be considered TEAEs. Summaries will be presented by system organ class and preferred term, and further by severity and relationship to study drug. Application site AEs and any TEAEs reported by $\geq 5\%$ of subjects will also be tabulated.
 - The proportion of subjects who discontinue treatment due to an adverse event will be presented.
- Concomitant medications will be classified according to the World Health Organization (WHO) Drug Dictionary and will be presented in data listings.

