6.3.2 Secondary Safety Endpoints

The secondary safety endpoints are as follows:

- Incidence and severity of application site adverse events (AEs);
- Incidence and severity of all AEs and their relationship to study drug;
- Incidence of clinically meaningful change from baseline in safety laboratory parameters, 12-lead electrocardiograms (ECG), and vital signs;

- Proportion of subjects who discontinue treatment due to an adverse event.

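### Treatment emergence is decided by onset date alone, so a pre-treatment AE that worsens on drug under its original date is missing from the TEAE tables

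*SAP*

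**What the plan says.** SAP 7.9.9.2 sets the rule: "Treatment-emergent AEs (TEAEs) are defined as AEs with an onset on or after the date of the first study drug application". The TEAE summaries by system organ class and preferred term, by severity, by relationship, and for terms reached by at least 5% of subjects rest on it.

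Protocol 11.5.1 agrees on timing: "All other AEs that start on or after first dose will be considered TEAEs". It then deals with earlier events: "AEs that occurred during the screening period will be listed separately and will not be included in the AE tabulations". It makes no exception for a screening event that later worsens.

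Protocol 10.3 collects AEs from consent. A change in status between consent and the first dose "will be recorded as a pre-treatment adverse event and severity will be assessed". Graded pre-treatment AEs will therefore exist in the database. Protocol 6.4 adds to them by having significant pre-dose examination findings entered as AEs.

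Two SAP tables are worded more widely. For serious events, "Serious AEs (SAEs) will be summarized by system organ class, preferred term, severity, and relationship to study drug", with no restriction to TEAEs. The table of AEs leading to treatment or study discontinuation has no such restriction either. SAP 7.9.9.2 also lists all AEs.

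The secondary endpoint served by these tables is given in SAP 6.3.2: "Incidence and severity of all AEs and their relationship to study drug".

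**The concern.** A TEAE table is meant to show what happened on drug. A mild event before dosing that becomes severe afterwards happened, in the sense that matters, on drug. A rule that looks only at the onset date misses it, and the matching protocol sentence keeps it out of the tabulations as well.

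The plan makes such events plausible. Screening lasts up to 30 days, AEs are recorded throughout it, several skin treatments are withdrawn before baseline, and pre-dose findings are entered as AEs.

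Safety is the only secondary objective, and the omission works in one direction. It can reduce the number of children with a TEAE, the maximum severity shown and the number of events judged related. It cannot increase them.

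**Working it through.** The documents give no AE rate, so there is no plan figure to reproduce. The check is of the text, followed by arithmetic for scale.

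**1. Search for a worsening rule.** SAP 7.9.9.2 tests onset date. Protocol 11.5.1 tests start. Protocol 10.3 speaks of events occurring after the first dose. None mentions an increase in severity. The protocol discusses worsening only for the atopic dermatitis (4.6.1.1) and the treatment area (6.9.3). No readable text tells sites to enter a worsened AE as a new record with a new onset date.

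**2. Apply the rules literally to four hypothetical records.**

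| Record | TEAE under SAP 7.9.9.2? | Where it appears |
|---|---|---|
| A. Starts Day 10, moderate | Yes | All relevant TEAE tables |
| B. Starts Day -7, mild; severe and probably related on Day 5; onset date unchanged | No | Listing only |
| C. As B, but becomes serious or leads to discontinuation | No | Listing; SAP SAE or discontinuation table as worded; kept out of tabulations by protocol 11.5.1 |
| D. As B, but the site opens a new record dated Day 5 | Yes | All relevant TEAE tables |

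B is the gap. The SAP's rule of taking each subject's most severe event does not recover it, because that rule chooses among events already in the TEAE summary. C shows that the two documents do not agree. D shows that the result depends on a site practice that neither document fixes.

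**3. Weight of one child.** Inputs are 32 subjects (SAP 4.2), about 45 registered (SAP 4.1), and the AE age subgroups of SAP 7.7 with the group sizes of SAP 4.1.2: about 8 aged 2-5 and 16 + 8 = 24 aged 6-17. One child as a share of N is 1/N:

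- 1/32 = 3.1%
- 1/45 = 2.2%
- 1/8 = 12.5%
- 1/24 = 4.2%

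**4. The 5% table.** At N = 32, 0.05 × 32 = 1.6, so a term needs 2 children. Losing one takes it from 2/32 = 6.3% to 1/32 = 3.1%. At N = 45, 0.05 × 45 = 2.25, so it needs 3. Losing one takes it from 3/45 = 6.7% to 2/45 = 4.4%. At either size, one omission can drop a term that only just qualifies.

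**5. Chance that it happens at all.** Let q be the share of children with an event of type B. This is an assumption. The chance that at least one of 32 is affected is 1 - (1 - q)^32:

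| Assumed q | At least one of 32 |
|---|---|
| 1% | 27% |
| 2% | 48% |
| 5% | 81% |
| 10% | 97% |

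If q is zero, so is the effect. The table shows only that a low rate could matter in a study this small.

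**The case against.** The strongest reply is that nothing is lost. All AEs are listed, the study is one-arm and descriptive, and listings for 32 to 45 children can be read case by case. That is true, but the endpoint is reported through tables, and a reader of those tables would not know to look in the listing.

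A reader might infer that even a serious worsening disappears from every table. The SAP does not support this, because its SAE and discontinuation tables are not limited to TEAEs. Protocol 11.3.1 lets the SAP modify the planned analysis, which favours the SAP wording. SAP section 5, however, declares no changes, so the conflict with protocol 11.5.1 stays open.

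A reader might also infer that the loss falls mainly on skin events, given the washout of topical treatments. The documents do not show this. Pruritus is an entry feature of the disease (protocol 6.3.2), and nothing says that a washout flare would be logged as a screening AE. Clinically infected disease is an exclusion, so a skin infection just before Day 1 may prevent dosing. Application-site events cannot precede an application. Protocol 6.4 and 6.18 also have post-dose examination findings and skin irritation recorded as AEs, which gives a partial route to a new record. That route covers certain findings and does not assign a new onset date, so the gap is narrower for skin but not closed.

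Finally, the frequency is unknown, and no expected number of missed children can be drawn from the documents. This objection stands in full.

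**Conclusion.** The point holds as a defect in a stated rule. Followed literally, SAP 7.9.9.2 and protocol 11.5.1 leave a pre-treatment AE that worsens on drug out of the TEAE tables whenever it keeps its original onset date. The resulting error is downward only.

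Its size cannot be estimated and may be zero. It depends on how many children have a graded AE still present at the first application, how many of those worsen, and whether sites open a new record. The per-child weights above are arithmetic on planned numbers; the safety population may differ from both 32 and 45.

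The rule also counts a Day 1 event that starts before the application, because it works by date. That is a separate matter in the opposite direction and does not offset this one.

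The change is worth making before the SAP is final, because it is cheap and removes dependence on site habit.

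**What to change.** - **SAP 7.9.9.2:** define TEAEs as AEs with onset on or after the first application, or AEs present before it that increase in severity or become serious on or after it. Tabulate them with the post-dose severity and relationship.
- **Protocol 11.5.1:** limit the exclusion from tabulations to screening AEs that did not worsen after the first dose.
- **SAE and discontinuation tables:** state that they include worsened events, so that SAP and protocol agree.
- **Recording:** choose one method. Either enter the worsening as a new record dated at the worsening, leaving the original as pre-treatment and not flagged as a TEAE, or keep a single record that carries the date of the severity change. Using both could flag two records for one event, although each subject would still be counted once per term in the severity and relationship summaries.

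The cost is a change to the SAP definition, a protocol clarification and one eCRF instruction. Pre-dose severity is already collected. The documents do not say whether the eCRF dates a change in severity, so the single-record method may need a field for it. TEAE counts may come out slightly less favourable.

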7.9.9.3 Clinical Laboratory Evaluations

Laboratory test results will be summarized with descriptive statistics at Baseline and Day 29. Additionally, change from baseline values will be summarized at Day 29, and shifts from Baseline to Day 29 in laboratory test results based on normal ranges will be summarized with frequency counts and percentages. Individual laboratory test results, including urine and serum pregnancy test results, will be presented in a by-subject listing.

7.9.9.4 Other Observations Related to Safety

7.9.9.4.1 ECG Measurements

ECGs will be performed in triplicate at Screening, Day 1, Day 15 and Day 29, and the following parameters will be measured for each ECG: heart rate, RR duration, QRS duration, PR duration, QT duration, QT interval corrected for heart rate using Bazett's formula (QTcB), and QT interval corrected for heart rate using Fridericia's formula (QTcF). For each parameter and each visit, the mean of all measurements collected at the visit will be calculated, so each subject will have one value associated with each ECG parameter at each visit.

Descriptive statistics at Baseline, Day 15, and Day 29 will be provided for each ECG parameter. Change from baseline values will be summarized at Day 15 and Day 29.

Individual ECG measurements, as well as means of triplicates, will be presented in a by-subject listing.

7.9.9.4.2 Vital Signs

Temperature, respiratory rate, heart rate, blood pressure, and weight will be summarized at each visit, and change from baseline values will be presented for post-baseline visits. Weight will be summarized at Baseline, Day 15, and Day 29, and all other vital signs will be summarized at Baseline, Day 8, Day 15, Day 22, and Day 29.

Heart rate and blood pressure measurements are collected in triplicate at each visit. Prior to computing summary statistics, the mean of each measurement will be calculated for each subject

at each visit. Summary statistics will be computed from each subject's mean heart rate and blood pressure values at each visit.

Individual vital sign data, as well as means of heart rate and blood pressure triplicates, will be presented in a by-subject listing.

7.9.9.4.3 Physical Examination

Physical examination data will be presented in a by-subject listing.

